APPENDIX 7 EASTERN COOPERATIVE ONCOLOGY GROUP (ECOG) PERFORMANCE STATUS

	ECOG PERFORMANCE STATUS ^a							
0	Fully active, able to carry on all pre-disease performance without restriction							
1	Restricted in physically strenuous activity but ambulatory and able to carry out work of a light or sedentary nature, eg, light house work, office work							
2	Ambulatory and capable of all selfcare but unable to carry out any work activities. Up and about more than 50% of waking hours							
3	Capable of only limited selfcare, confined to bed or chair more than 50% of waking hours							
4	Completely disabled. Cannot carry on any selfcare. Totally confined to bed or chair							
5	Dead							

^a Oken MM, Creech RH, Tormey DC, Horton J, Davis TE, McFadden ET, and Carbone PP. Toxicity and Response Criteria of the Eastern Cooperative Oncology Group. Am J Clin Oncol 1982; 5: 649-655.

APPENDIX 8 CONSORT PUBLISHING REQUIREMENTS

The Consolidated Standards of Reporting Trials (CONSORT) encompasses various initiatives developed by the CONSORT Group to alleviate the problems arising from inadequate reporting of randomized controlled trials.

The CONSORT Statement

The main product of CONSORT is the CONSORT Statement, which is an evidence-based, minimum set of recommendations for reporting randomized trials. It offers a standard way for authors to prepare reports of trial findings, facilitating their complete and transparent reporting, and aiding their critical appraisal and interpretation. CONSORT 2010 is the current version of the statement and supersedes the 2001 and 1996 versions.

The CONSORT Statement comprises a 25-item checklist and a flow diagram. The checklist items focus on reporting how the trial was designed, analyzed, and interpreted. The flow diagram displays the progress of all participants through the trial. The checklist and flow diagram are freely available for viewing and downloading at the CONSORT website (http://www.consort-statement.org/consort-2010). The CONSORT Statement is endorsed by general medical journals, specialty medical journals, and leading editorial organizations. CONSORT is part of a broader effort, to improve the reporting of different types of health research, and indeed, to improve the quality of research used in decision-making in healthcare.

CONSORT 2010 Guideline

The CONSORT (CONsolidated Standards of Reporting Trials) 2010 guideline is intended to improve the reporting of parallel-group randomized controlled trial (RCT), enabling readers to understand a trial's design, conduct, analysis and interpretation, and to assess the validity of its results. This can only be achieved through complete adherence and transparency by authors. CONSORT 2010 was developed through collaboration and consensus between clinical trial methodologists, guideline developers, knowledge translation specialists, and journal editors (see CONSORT group). CONSORT 2010 is the current version of the guideline and supersedes the 2001 and 1996 versions.

CONSORT "Explanation and Elaboration" Document

The CONSORT "Explanation and Elaboration" document explains and illustrates the principles underlying the CONSORT Statement, and should preferably be used in conjunction with the CONSORT Statement. In addition, extensions of the CONSORT Statement have been developed to give additional guidance for RCTs with specific designs, data and interventions. The CONSORT website (http://www.consort-statement.org/consort-2010) contains the current definitive version of the CONSORT 2010 Statement and up-to-date information on extensions.

APPENDIX 9 NEW YORK HEART ASSOCIATION (NYHA) FUNCTIONAL CLASSIFICATION

Heart failure is usually classified according to the severity of their symptoms. The table below describes the most commonly used classification system, the New York Heart Association (NYHA) Functional Classification. It places patients in one of four categories based on how much they are limited during physical activity.

Class	Patient Symptoms
Ι	No limitation of physical activity. Ordinary physical activity does not cause undue fatigue, palpitation, dyspnea (shortness of breath).
II	Slight limitation of physical activity. Comfortable at rest. Ordinary physical activity results in fatigue, palpitation, dyspnea (shortness of breath).
III	Marked limitation of physical activity. Comfortable at rest. Less than ordinary activity causes fatigue, palpitation, or dyspnea.
IV	Unable to carry on any physical activity without discomfort. Symptoms of heart failure at rest. If any physical activity is undertaken, discomfort increases.

Class	Objective Assessment							
А	No objective evidence of cardiovascular disease. No symptoms and no limitation in ordinary physical activity.							
В	Objective evidence of minimal cardiovascular disease. Mild symptoms and slight limitation during ordinary activity. Comfortable at rest.							
С	Objective evidence of moderately severe cardiovascular disease. Marked limitation in activity due to symptoms, even during less- than-ordinary activity. Comfortable only at rest.							
D	Objective evidence of severe cardiovascular disease. Severe limitations. Experiences symptoms even while at rest.							

APPENDIX 10 STATISTICAL METHODOLOGY

STATISTICAL DETAILS FOR BAYESIAN LOGISTIC REGRESSION MODEL AND PRIORS FOR DOSE ESCALATION AND SAFETY MONITORING

1 MODEL SETUP FOR BMS-986226 MONOTHERAPY

1.1 Monotherapy Methodology Description

An adaptive 2-parameter Bayesian Logistic Regression Model (BLRM) guided by the escalation with overdose control (EWOC) principle^{1,2,3} will be used to guide the dose escalation of BMS-986226 monotherapy in the monotherapy phase, providing dose recommendation during dose escalation.

The BLRM will be fitted on the dose-limiting toxicity (DLT) data during the first 5 weeks of treatment accumulated throughout the dose escalation to model the dose-toxicity relationship of BMS-986226 in the monotherapy dose escalation phase.

The dose-toxicity relationships for BMS-986226 monotherapy is assumed to follow a logistic model:

$$logit(p_i) = log(\alpha_1) + \beta_1 log(\frac{d_{1i}}{d_1^*}),$$

where p_i is the probability of toxicity at dose level d_{1i} . Note that the α_1 and β_1 parameters are assumed positive, and d_1^* is the reference dose for BMS-986226 (please refer to the meaning of α_1 and β_1 in Section 1.2 for detailed implementation).

1.2 Prior Specification for BMS-986226 Monotherapy

The Bayesian approach requires the specification of prior distributions for model parameters, which include parameters (α_1 , β_1) for BMS-986226. The prior distributions for BMS-986226 single agent activity were derived using a weakly informative prior, as well as discussion with the Bristol-Myers Squibb (BMS) clinical team. Details are provided below.

Weakly Informative Prior

- The median DLT rate at the reference dose (BMS-986226 at 800 mg every 4 weeks) was assumed to be 30%, that is, mean $(\log(\alpha_1)) = \text{logit}(0.3) = \log(0.3/(1-0.3)) = -0.847$.
- A doubling in dose was assumed to double the odds of DLT, that is, mean $(\log(\beta_1)) = 0$.

The standard deviation (sd) of $log(\alpha_1)$ was set to 1.53 using the following steps:

- If the toxicity probability range was set to be [1%, 99%], then the toxicity interval would be logit (0.99)-logit (0.01) = 9.19.
- To cover 99.7% of the variance, the toxicity interval will cover $6 \times sd (\log(\alpha_1))$, which gives us $sd (\log(\alpha_1)) = 9.19/6 = 1.53$.

Correspondingly, the standard deviation of $log(\beta_1)$ was set to 1, which allows for considerably larger prior uncertainty for the dose toxicity.

- 1) The correlation between $\log(\alpha_1)$ and $\log(\beta_1)$ was set to 0.
- 2) $Log(\alpha_1)$ and $log(\beta_1)$ follow a bivariate normal distribution.

Through those steps, the prior obtained is given in Table 1.2-1.

Table 1.2-1:Prior Distribution for Model Parameters for BMS-986226

Parameter	Means	Standard Deviations	Correlation
$\log(\alpha_1), \log(\beta_1)$	(-0.847, 0)	(1.53, 1)	0

This prior will be fitted into EAST[®] v6.3.1 Dose Escalation Module by Cytel for the Monotherapy Escalation of BMS-986226 as stated in model setup section.

2 DECISION RULE FOR DOSE ESCALATION AND SIMULATION

Dose escalation recommendations for BMS-986226 monotherapy will be based on the inference from the Bayesian posterior and the probability that the true DLT rate for each dose lies in 1 of the following categories:

- [0%, 16%) under-dosing
- [16%, 33%) targeted toxicity
- [33%, 100%] excessive toxicity

Note: "[" or "]" is inclusive of the respective endpoint, and "(" or ")" exclusive of the respective endpoint.

These boundaries are similar to the toxicity boundaries used by a rule-based design (ie, 3 + 3 design) in that a minimum is set at 16% (~ 1 in 6) DLT rate and a maximum at 33% (~ 2 in 6) DLT rate. Following the principle of EWOC, dose recommendations for the next cohort will be based on the Bayesian model after DLT information becomes available during the DLT period, accounting for all of the available data from the administered doses, and the candidate doses are the ones fulfilling the overdose criterion that there is less than 30% chance of excessive toxicity. Only the candidate doses will be considered for the next cohort. While the Bayesian model will use DLT information from the DLT period only, clinical assessment will take into consideration of the totality of available data including pharmacokinetics (PK)/pharmacodynamics from all treated participants.

Stopping Rules:

The following is the general stopping rules of BLRM (-Copula) during Dose Escalation:

• If all of 30 DLT evaluable participants are treated.

- If all of the current pre-specified doses are considered intolerable according to the pre-specified cutoff (ie, EWOC criteria), then the model will recommend stopping the current dose level and a new dose level lower than the current lowest dose level will need to be identified.
- The maximum number of DLT-evaluable participants in a dose level will be 12. This limit is set to avoid instances in which the model could recommend adding subjects indefinitely to a specific dose level due to uncertainty in the tolerability profile.
- If, for a specific dose level, 6 subjects have been treated and the chance of determining that the dose level to be the "target" dose is > 50%, then the model will suggest to stop and declare the current dose level to be the maximum tolerated dose (MTD).

Model-recommended MTD:

The MTD is the dose that satisfies the following 3 conditions:

- 1) The empirical posterior probability that the 'DLT rate of 16% -< 33%' is greater than 50%.
- This probability needs to be the largest among the dose levels that satisfy the EWOC condition (ie, the probability that 'DLT rate ≥ 33%' must be less than 30%).
- 3) Minimum number of participants (ie, 6) were treated at this dose level.

Final MTD:

The final recommended MTD in Part A will be based on the recommendation from the BLRM and overall clinical assessment of all available safety, PK/pharmacodynamics, and efficacy data. Lower doses of BMS-986226 may be tested if none of the planned doses are found to be tolerable. Such decisions will be made after discussion and agreement between the investigators and the BMS Medical Monitor.

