2.1 Simulation Parameters

One thousand trial simulations will be used for each scenario. All simulations will be run using EAST v6.3.1 software for BLRM model for the BMS-986226 monotherapy. The number of subjects to be treated in each cohort in a specific dose level and the stopping rules used to declare MTD are defined as:

- Fixed cohort size: 3
- Probability of overdosing: < 30%
- Probability of achieving the target toxicity: > 50%
- Maximum number of participants treated: 30
- Minimum number of participants treated at a given dose level in order to declare MTD: 6
- Maximum number of participants at a dose:12

The provisional dose levels for BMS-986226 monotherapy are 25 mg, 80 mg, 200 mg, 400 mg, and 800 mg.

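### Appendix 10's stopping bullet for declaring the MTD omits the overdose and best-dose conditions of the plan's own MTD definition, and the two can disagree on reachable data

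*Combined protocol and SAP*

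**What the plan says.** Appendix 10, section 2 (Decision Rule for Dose Escalation and Simulation), gives four general stopping rules. The fourth has two triggers: that "6 subjects have been treated and the chance of determining that the dose level to be the" target dose is above 50%. When both are met, "then the model will suggest to stop and declare the current dose level to be the maximum tolerated dose (MTD".

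The next paragraph of the same section defines the model-recommended MTD by three conditions:

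1. "The empirical posterior probability that the 'DLT rate of 16% -< 33%' is greater than 50" percent.
2. "This probability needs to be the largest among the dose levels that satisfy the EWOC condition", where EWOC is spelled out as "ie, the probability that 'DLT rate ≥ 33%' must be less than 30" percent.
3. "Minimum number of participants (ie, 6) were treated at this dose level".

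Protocol section 10.1.1 gives the same three conditions. Appendix 10, section 2.1, introduces its simulation settings by saying that "the stopping rules used to declare MTD are defined as" in the list that follows. That list includes "Probability of overdosing: < 30" percent, beside the 50% target probability and the minimum of six.

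**The concern.** The bullet carries conditions 1 and 3 of the definition but not condition 2, which has two parts: the overdose limit, and the comparison with the other admissible doses. A target probability above 50% does not imply an overdose probability below 30%, because the two need only sum to at most 1. The bullet can therefore name as MTD a dose that the definition excludes.

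This is a pre-specified rule for the main dose-finding decision of a first-in-human trial, and the plan gives two versions of it. The declaration also has some bearing on dosing. Section 10.1.1 allows further participants, to a total of 12, at or below the estimated MTD, and the same section says EWOC caps the probability of a DLT rate above 33% at 30%.

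**Working it through.** **Inputs (Appendix 10).** Section 1.1: logit(p) = log(α₁) + β₁·log(d/800). Section 1.2: log(α₁) ~ N(−0.847, 1.53²) and log(β₁) ~ N(0, 1²), correlation 0. Section 2: target interval [16%, 33%), overdose interval [33%, 100%]. Section 2.1: doses 25, 80, 200, 400 and 800 mg, cohorts of 3, at most 12 per dose and 30 in total.

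**Method.** The posterior is the prior times the product over doses of p^y·(1−p)^(n−y), integrated on a grid. Target is P(0.16 ≤ p < 0.33) and overdose is P(p ≥ 0.33). Next dose is the EWOC-admissible dose with the largest target probability, moving up at most one level. Section 3.1 rules out the jump from 25 to 400 mg.

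**Reproducing the plan's figures.** Section 3 works an example with 0/3 at 25 mg and 1/3 at 80 mg. It states target probabilities of 0.372 at 200 mg and 0.311 at 80 mg, with 400 and 800 mg excluded. The grid gives 0.360 and 0.299, and overdose probabilities of 0.28, 0.47 and 0.63 at 200, 400 and 800 mg. The exclusions and the recommendation of 200 mg agree. The target probabilities differ by 0.012. After 0/3 at 25 mg the grid's unrestricted choice is 400 mg, as section 3.1 states.

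**Example 1, continuing the plan's own example.**

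- 0/3 at 200 mg: 400 mg has target 0.38 and overdose 0.26, the best admissible dose.
- 1/3 at 400 mg: target 0.46, overdose 0.297, still the best admissible dose.
- 2/6 at 400 mg: target 0.51, overdose 0.323.

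The bullet's triggers are met at 400 mg (n = 6, 0.51 > 0.50). Condition 2 fails (0.323 > 0.30). The best admissible dose is 200 mg, with target 0.49 and n = 3, so no dose meets the definition.

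**Example 2, wider margins.** Take 0/3 at 25 mg, 0/3 at 80 mg and 1/6 at 200 mg, then 0/3 at 400 mg, 2/3 at 800 mg, and 2/3 on returning to 400 mg. At 400 mg (2/6) target is 0.53 and overdose 0.378. The bullet names 400 mg and the definition does not.

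**Example 3, no step close to the EWOC limit.** Take 0/3 at 25, 80, 200 and 400 mg. At 800 mg overdose is 0.22 before dosing, 0.27 after 1/3 and 0.10 after 1/6. After 3/9 target is 0.508 and overdose 0.329. The bullet names 800 mg and the definition excludes it.

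**Sensitivity.** The 0.012 gap from the plan's figures is about as large as the margin on the 50% threshold in examples 1 and 3. Example 2 has margins of 0.03 on target and 0.08 on overdose, but its path passes within 0.005 of the EWOC limit at two steps (0.304 for 400 mg after 1/3 at 200 mg, 0.296 for 800 mg). The conclusion does not rest on one of these near-threshold values alone.

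**Frequency, illustrative only.** An exact enumeration of trials without dose skipping, stopping on the bullet as written, declares an EWOC-excluded dose in 10.2%, 11.2%, 8.5%, 7.8% and 4.7% of trials in the five scenarios of Table 2.2.1-1 (prior, flatter, narrow, all low, all high). Under the full definition the share is 0% by construction. The enumeration does not replicate the table, which allowed dose skipping in EAST. Under the full definition it leaves about 41% of prior-scenario trials without an MTD, against 0.9% in the table.

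**The case against.** The strongest reply is that the overdose limit is already part of the MTD rules. It stands in the definition directly below the bullet, in section 10.1.1 and in section 2.1, so an implementer using the section 2.1 settings would apply it and the bullet is only an abbreviation. That stands as far as it goes: the limit is not missing from the plan. It does not say which text governs when they disagree, and the bullet contains no cross-reference.

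Three stronger readings are tempting, and the documents do not support them.

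- *The MTD is declared on target probability alone.* The bullet also needs six participants at the dose.
- *The trial escalates without overdose control.* Section 2 restricts next-cohort doses to those passing EWOC, whatever the bullet says. The bullet is also a suggestion by the model: the final MTD rests on the model and on overall clinical assessment.
- *A wrongly named dose passes unchecked into Parts B to E.* Parts B and C start one level below a monotherapy dose that has cleared the DLT period (section 5.1), combination doses must meet EWOC in their own model (Appendix 10, section 5), and Parts D and E await a protocol revision (section 5.1.2.4).

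The checked examples exceed the limit moderately, at 0.32 to 0.38 against 0.30. Clinical review is a real safeguard, but it does not settle which of two conflicting rules the model applies.

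**Conclusion.** The point holds as an internal inconsistency. On reachable data the fourth stopping bullet names a model MTD that the definition in the same section, and in section 10.1.1, forbids. This is more than missing detail, because two stated rules give different answers. It rests on the text of the bullet and on the Appendix 10 prior. The posterior for a given dataset does not depend on any simulation set-up; whether that dataset is reached depends on the allocation rule described above. The frequency, roughly 5% to 11% of trials in the enumeration, is an illustration and not an estimate of the trial's operating characteristics. It is not established which rule produced Table 2.2.1-1.

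**What to change.** Reconcile the passages. The simplest change is one sentence: the fourth bullet applies only when the current dose meets all three conditions of the model-recommended MTD, and otherwise the ordinary next-dose rule continues. State beside Table 2.2.1-1 which declaration rule was simulated, and rerun it if it was not this one.

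The drafting cost is small. The operating cost is that some trials will need further cohorts or will end without a model-recommended MTD. In example 1, 200 mg has three participants, so at least one more cohort of 3 is needed before any dose can qualify. In example 3, 400 mg has a target probability of only 0.18 with three participants, so an extra cohort may still leave no qualifying dose. The rerun should report the share of trials with no MTD.

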2.1 Simulation Parameters

One thousand trial simulations will be used for each scenario. All simulations will be run using EAST v6.3.1 software for BLRM model for the BMS-986226 monotherapy. The number of subjects to be treated in each cohort in a specific dose level and the stopping rules used to declare MTD are defined as:

- Fixed cohort size: 3
- Probability of overdosing: < 30%
- Probability of achieving the target toxicity: > 50%
- Maximum number of participants treated: 30
- Minimum number of participants treated at a given dose level in order to declare MTD: 6
- Maximum number of participants at a dose:12

The provisional dose levels for BMS-986226 monotherapy are 25 mg, 80 mg, 200 mg, 400 mg, and 800 mg.

2.2 Operating Characteristics

Section 2.2.1 demonstrates operating characteristics of BLRM for monotherapy.

2.2.1 Operating Characteristics of BLRM for Monotherapy

Five scenarios were investigated by selecting (1) dose-DLT relationship derived by prior, (2) dose-DLT curve flatter than the one by the prior; (3) narrow safety window in order to explore how EWOC limits the risk of exposing participants from a toxic dose level, (4) all doses below the target toxicity, and (5) all doses above the target toxicity. Simulations were performed using EAST v6 BLRM which allows dose skipping.

For scenario (1), the % DLT by prior was derived using the model solving for the probability, p_i at the ith dose.

$$\operatorname{logit}(p_i) = \log(\alpha_1) + \beta_1 \log(\frac{d_{1i}}{d_1^*})$$

The model can be re-written as follows.

$$p_{i} = \frac{1}{1 + \exp\left(-\log(\alpha_{1}) - \beta_{1}\log(\frac{d_{1i}}{d_{1}^{*}})\right)}$$

Using the estimates in Section 1.2, ie, $\log(\alpha_1) = -0.847$ and $\beta_1 = 1, d_1^* = 800$ mg, the prior probability of DLTs at dose 25, 80, 200, 400, and 800 mg is 0.01, 0.04, 0.1, 0.18, and 0.30, respectively.

BMS-MTD Fitted Toxicity Avg 986226 Not Scenario 25 80 200 400 800 Median Observed No. of Selected Dose Patients (%) MTD (%) (**mg**) % DLT 1 4 10 18 30 0.9 9.9 % MTD 0 61 28.2 0 698.7 17.3 18.2 By prior 0.5 2.0 8.2 # Pts 3.1 4.4 0 # DLTs 0 0.2 1.5 1.4 % DLT 10 15 20 25 30 Flatter than % MTD 3.9 11.9 22.2 38.5 16.9 6.6 510.4 22.4 17.4 the one by # Pts 4.1 2.0 2.7 5.8 2.7 the prior 0.4 0.3 0.6 0.8 # DLTs 1.4 % DLT 3 7 18 80 31 Narrow safety % MTD 0.4 7.9 40.7 49.8 0.2 1 443.4 23.2 18.3 window 1.9 # Pts 3.4 4.9 7.1 1.1

Table 2.2.1-1:Simulation Results of BLRM for Monotherapy

Scenario	BMS- 986226 Dose (mg)	25	80	200	400	800	MTD Not Selected (%)	Fitted Median MTD	Toxicity Observed (%)	Avg No. of Patients
	# DLTs	0.1	0.1	0.9	2.2	0.9				
	% DLT	1	5	10	15	20				
A 11 Jan	% MTD	0.1	0.8	5.4	39.2	54.3	0.2	925.1	13.9	18.4
All low	# Pts	3.1	0.3	1.3	7.0	6.8				
	# DLTs	0	0	0.1	1.0	1.3				
	% DLT	45	50	60	75	80				
	% MTD	11.6	2.6	0.7	0.1	0	85	10.7	57.8	7.0
All high	# Pts	5.2	1	0.26	0.6	0				
	# DLTs	2.3	0.5	0.1	0.5	0				

 Table 2.2.1-1:
 Simulation Results of BLRM for Monotherapy

% DLT, true DLT rate; % MTD, proportion of the dose selected as the MTD; # Pts, average number of participants by assuming 3 participants for skipped dose level where the true toxicity rate is below the target rate; # DLTs, average number of DLTs by assuming no DLT for skipped dose level where the true toxicity rate is below the target rate; Fitted MTD: fitted MTD at 30% as the target toxicity rate; % toxicity observed, average proportion of DLTs given the doses were tried

The average sample size in this simulation was observed to be no more than 20 participants. The results for the scenarios of narrow safety window and all high show how the EWOC principle limits the risk of exposing participants from a toxic dose level. Overall, the scenarios illustrated above demonstrate that the model performs well in the hypothetical scenarios investigated.

3 INTERIM MONITORING CASE STUDY TO ILLUSTRATE PROVISION OF DOSE RECOMMENDATIONS DURING DOSE-ESCALATION

In order to provide a comprehensive view of the dynamics of the models, different hypothetical scenarios exploring all possibilities are examined. For the simplicity of illustration purposes, a static cohort size of 3 subjects is applied for dose levels 25 mg, 80 mg, 200 mg, 400 mg, and 800 mg in the BMS-986226 monotherapy. This cohort size could vary during the actual clinical trial, and the BLRM models are designed to fit various different cohort sizes, adaptively. In general, there are 4 possible scenarios for a specific dose level, which are 0 DLT observed in 3 total subjects in that cohort (denoted as 0/3), 1 DLT observed in 3 subjects (1/3), 2 DLTs observed in 3 subjects (2/3), and 3 DLTs observed in 3 subjects (3/3).

During interim monitoring, posterior probabilities will be updated when there is new DLT information available. The following three visualization plots will be produced to reflect the real time dose-DLT relationship, to quantify benefit (in the form of target dosing) and risk (in the form of overdosing and underdosing) during model's recommendation process, and to facilitate clinical team's interpretation of the model recommendations for the final decision making:

- Dose-DLT profile for the doses ranging between 0 mg and 800 mg (Figure 3-1).
- Stacking histograms displaying predictive probabilities on DLT rates classified into 3 different categories (Underdosing, Target dosing, and Overdosing) (Figure 3-2).
- Box plots summarizing the Markov Chain Monte Carlo samples of predicted DLT rates for the 5 pre-specified dose levels (Figure 3-3).

In the following illustrations, Figure 3-1 to Figure 3-3 are produced using a hypothetical example assuming 0/3 DLTs observed in the 25-mg cohort and 1/3 DLTs observed in the 80-mg cohort.

Abbreviations: DLT = dose-limiting toxicity; L = low boundary; U = upper boundary.

Interpretation and usage of Figure 3-1:

Figure 3-1 is a snapshot of an updated dose-DLT profile with DLT information available at dose level 80 mg. The dose-DLT profile is captured with a continuous dose spectrum ranging from 0 mg to 800 mg. For each dose within the range, there is a corresponding distribution of the predicted DLT rates calculated from the posterior samples of the model parameters. This figure will be updated each time when new DLT information becomes available.

In Figure 3-1, there are 3 different quantiles (2.5%, 50%, and 97.5%) plotted to characterize the current trend of the toxicity profile (as shown by the 50% quantile), as well as the variation of the

dose-DLT profile (as shown by the 2.5% percentile and the 97.5% percentile), according to the accumulation of DLT data from all previous and current dose levels. The toxicity boundaries (low boundary 0.16 and high boundary 0.33) are illustrated in two dotted horizontal lines to benchmark the way, in which the dose-DLT profile is trending.

Intermediate dose levels can be identified using different boundary cutoffs. For example, using the 50% percentile curve (green highlight), which represents the nearly average DLT distribution for each dose level, the 100 mg could be a potential intermediate dose level corresponding to the lower pre-specified DLT rate boundary of 0.16, and the 450 mg could be a fitted MTD dose level associated with the upper boundary of 0.33.

Moreover, if all of the current pre-specified doses are considered intolerable (overdosing probabilities > 0.3, a case not shown on the current Figure 3-1), the model will recommend to stop the current dose level, and the clinical team can leverage the current updated dose-DLT curve to pinpoint a new dose, which is lower than pre-specified lowest dose (25 mg) by using the DLT rate boundaries.

Figure 3-2:Updated Stacking Histogram after Incorporating Prior Information
and All Previous DLT Information up to 80 mg Monotherapy Data to
Classify Predicted DLT Rates Into 3 Categories (Under Target,
Target Interval and Over Target)

Interpretation and usage of Figure 3-2:

Figure 3-2 is a snapshot of stacking histogram with DLT information available at dose level 80 mg for the combination studies. This figure will be updated each time when new DLT information

Revised Protocol No.: 04 Date: 31-May-2019

Approved v 5.0

becomes available in the combination setting. Similar graphs will also be produced for the BMS-986226 monotherapy.

When recommending the next dose level, the model will first exclude doses that are intolerable (with overdosing probabilities > 30%, the rate that has been specified for BMS-986226 in combination with ipilimumab). Among those qualified candidate doses that are considered "tolerable", the model will select the dose that maximizes the probability of being within the target toxicity range (DLT rate of 16% up to 33%).

As illustrated in Figure 3-2, when there is 0 DLT observed out of 3 subjects for the dose level 25 mg and 1 DLT out of 3 subjects for the dose level 80 mg, the distribution of predicted DLT rates will be characterized into possibilities falling into 3 different categories. First, dose levels of 400 mg and 800 mg for BMS-986226 are excluded according to the higher-than-cutoff (0.3 for mono therapy) overdosing probabilities. Among the remainder of tolerable dose levels (25, 80, and 200 mg), the BLRM-Copula model recommends the dose that maximizes the probability of being within the target dosing interval. Therefore, the model's recommendation would be to escalate to 200 mg, which is associated with the highest target dosing probability of 0.372 compared with that of 80 mg (0.311).

Similarly (although not shown on Figure 3-2), according to the rules specified above, the model could possibly recommend to de-escalate to a lower dose level than current treated dose level, extend the current dose level, or even recommend to stop and identify a new dose level lower than 80 mg, the lowest pre-specified dose level. Please refer to description of Figure 3-1 for details on how to specify the new dose levels.

Interpretation and usage of Figure 3-3:

Figure 3-3 is a snapshot with DLT information available at dose level 80 mg for the combination setting. The dose-DLT distributions calculated from the posterior samples of the model parameters are characterized in the format of boxplots for the pre-specified dose levels. This figure will be updated each time when there is new DLT information available. Similar graphs will also be produced for the BMS-986226 monotherapy.

This plot supplements the information provided in Figure 3-1. It allows for a more in-depth and focused visualization of general trend of dose-DLT relationship, as well as the magnitude and variability in the DLT rates for each pre-specified dose level.

